11.2 Sample Size Considerations

A previous study of collagen deposition in humans conducted in the [name] lab found a standard deviation for collagen deposition of 0.81 (log scale). We can use this estimate to examine the power of a 2 sample *t*-test to find differences between 2 groups of 25 subjects as this power depends on the magnitude of the difference between the 2 groups.

Difference in average of collagen	0.5	0.6	0.7	0.8
Power	0.59	0.75	0.86	0.94

11.3 Enrollment/Stratification/Randomization/Blinding Procedures

HIV infected subjects will be randomized to receive losartan or placebo in a 1:1 manner using ordinary methods for generating random deviates. Study staff (other than those in the IDS pharmacy) and participants will be blinded to the random assignments of all HIV infected study participants. All study drug will be supplied in identical containers.

The two-photon microscopy sub-study of the HIV infected subjects requires 5 participants on losartan and 5 on placebo. Investigators are blinded to treatment assignment. To be able to ensure we have the 5 on losartan and 5 on placebo we will give the list of all subjects who agree to the sub-study to the investigation pharmacist who maintains the blind. They will identify the ten participants we should use for the sub-study.

Blinding will be maintained until all data are entered into the study database, all study endpoint data and other data included in the final analysis have been verified and the data are ready for final analysis. This will be explained to participants as part of the study. Unblinding will occur according to standard operating procedures as per section 9.13.

11.4 Maintenance of Treatment Randomization Codes

The investigational pharmacy at the University of Minnesota Medical Center will make randomization assignments and will maintain the treatment randomization codes. They will be responsible for informing the DSMB of these codes for any interim analysis that is planned.

11.5 Final Analysis Plan

As detailed in section 11.1, once all of the data is available, mixed effects models will be used to test for differences between treatment groups using standard methods for the analysis of longitudinal data. Conventional significance levels will be used and the fit of the models will be assessed using standard tools (e.g. residual plots).

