4. STUDY DESIGN

4.1 Description of the Study Design:

This is a randomized, double-blind, placebo-controlled trial of 50 HIV-1 infected individuals on stable ART randomized in a 1:1 ratio to losartan (50 mg orally daily titrated to 100 mg daily) vs placebo for 30 months. We plan to enroll a total of 63 HIV infected subjects to ensure that 50 complete the protocol. All HIV infected subjects will undergo biopsies of inguinal lymph node (LN) and gut associated lymphatic tissue (GALT) for primary endpoint analysis at baseline, 12 and 30 months after study enrollment. Blood will be collected at least quarterly throughout the study and an intensive blood pharmacokinetic (PK) study will be conducted at month 1. All HIV infected subjects will be vaccinated with the quadrivalent human papillomavirus (HPV) vaccine at months 23, 25 and 29.5. 5 HIV uninfected control subjects will also be enrolled. They will not receive study agents or HPV vaccination and will undergo blood draw and inguinal LN biopsy at one time point only. We anticipate completing subject enrollment over a 14 month period and plan to complete all subject follow up 44 months after the first subject is enrolled.

4.2 Study Endpoints:

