4.2.1 Primary Endpoint

The primary endpoint is to determine the impact of losartan on LT fibrosis in HIV infected, ART treated adults. This will be determined by measuring the amount of collagen deposition in LT and the integrity of the FRCN using immunohistochemistry (IHC) and quantitative image analysis (QIA).

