7.3.3.3 Colonoscopy with Ileal and Rectal Biopsies

Approximately 20 snip biopsies of ileum and rectum will be obtained. Half of these samples will be placed in 4% PFA followed by 80% ethanol. They will then be paraffin embedded and used in IHC and ISH studies. The remaining samples will be immediately placed into RPMI and transferred to the [name] lab for preparation of cell suspensions. Distribution of isolated cells is detailed in the Specimen Management Plan in the study files.

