11. STATISTICAL CONSIDERATIONS

11.1 Overview and General Design Issues

From the perspective of statistical analysis, the aims of the proposed study are all quite similar: to determine if a randomized intervention has an impact on a longitudinally observed outcome. Despite this similarity, there are differences in the frequency with which some outcomes of interest will be observed and this will impact the details of how the analysis will be conducted. In particular, some variables will be measured quarterly (those that are assessed in peripheral blood, such as LPS, IL-6, TNF and ICAM-1) while those variables assessed via biopsy (such as the number of Ki67+ cells and the magnitude of the FDC pool) will only be available at baseline, and 12 and 30 months after initiating treatment with losartan. The approach that will be used to test for treatment effects in both scenarios will involve fitting mixed models with treatment group indicators, time effects and interactions between time and treatment group to allow for testing for differences in rates of change between the 2 groups. What will differ between the 2 scenarios will be the modeling strategy, as the data that is more frequently observed will permit more sophisticated modeling strategies. These strategies include allowing for nonlinear trajectories via cubic splines and more flexible covariance structures. These models will be fit via restricted maximum likelihood and tests for differences between the treatment groups will be conducted using Wald tests. Standard diagnostics will be employed to assess the adequacy of the fit and remedial measures (e.g. transforming the outcome variable) will be employed as appropriate. The most current version of the statistical software R and the lme package will be used to fit models and examine the data. With 25 subjects per group the study should have adequate power to find strong effects; however losartan has not previously been used in the proposed context.

Analysis of data from the MRI substudy will be descriptive in nature. We are seeking to identify MRI methods that will render an image of the inguinal lymph node that is about to be excised. We will compare

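### The primary endpoint combines two measures and two tissues, but the plan names no lead test, success rule or multiplicity control

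*Combined protocol and SAP*

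**What the plan says.** Section 4.2.1 says that the primary endpoint will be determined by "measuring the amount of collagen deposition in LT and the integrity of the FRCN". The two measures are not ranked and no composite is defined; the Protocol Summary and section 3.1 read the same way.

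Section 4.1 has both inguinal lymph node and gut sampled for this purpose: "gut associated lymphatic tissue (GALT) for primary endpoint analysis at baseline, 12 and 30 months after study enrollment". The gut material comes from two sites. Section 7.3.3.3 states: "Approximately 20 snip biopsies of ileum and rectum will be obtained". It does not say whether the sites are pooled.

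For the analysis, section 11.1 plans mixed models with treatment, time and their interaction, and "tests for differences between the treatment groups will be conducted using Wald tests". Section 11.5 adds only "Conventional significance levels will be used". Sections 4.2 and 11 contain no numeric alpha, lead measure, lead tissue, hierarchy, co-primary rule or adjustment.

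Section 11.2 gives power for collagen alone, using a standard deviation of 0.81 on the log scale and 25 subjects per group. It names neither a tissue nor a time point. FRCn integrity has no power basis.

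**The concern.** A claim that losartan reduces lymphoid tissue fibrosis could rest on collagen or FRCn integrity, in lymph node or gut. As the plan stands, the result called primary could be chosen after the data are seen without contradicting any written rule. If one success among several is enough, the chance of a false primary claim is higher than for a single test.

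The gap also reaches monitoring. Section 10.1.1 asks the DSMB to watch treatment differences in the main efficacy outcomes, with efficacy stopping to follow plans laid down in the protocol. The protocol does not say which measure that is.

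**Working it through.** **1. Recover the significance level.** The plan gives no number, so I tested two-sided 0.05 against the power table in section 11.2. Inputs from 11.2: n = 25 per group, SD = 0.81, differences 0.5 to 0.8.

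Standard error = 0.81 × √(2/25) = 0.229. Power ≈ Φ(difference/0.229 − 1.96).

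| Difference | Plan | Two-sided 0.05, normal | Two-sided 0.05, exact t | One-sided 0.05, normal |
|---|---|---|---|---|
| 0.5 | 0.59 | 0.588 | 0.571 | 0.705 |
| 0.6 | 0.75 | 0.745 | 0.728 | 0.835 |
| 0.7 | 0.86 | 0.863 | 0.849 | 0.921 |
| 0.8 | 0.94 | 0.937 | 0.928 | 0.968 |

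Two-sided 0.05 with the normal approximation reproduces the table; one-sided 0.05 does not. I take two-sided 0.05 as the conventional level.

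**2. Count the tests.** The two named measures give 2 tests. Collagen in both tissues plus FRCn in lymph node gives 3. Both measures in both tissues gives 4.

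**3. Family-wise error if any one test suffices.** All nulls are true. For k independent tests the error is 1 − 0.95^k:

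- k = 2: 1 − 0.9025 = 9.8%
- k = 3: 1 − 0.8574 = 14.3%
- k = 4: 1 − 0.8145 = 18.5%

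For correlated tests, assume normal test statistics with equal pairwise correlation ρ. The documents give no correlation, so ρ is an assumption shown over a range. The error is 1 − ∫ [Φ((1.96 − x√ρ)/√(1−ρ)) − Φ((−1.96 − x√ρ)/√(1−ρ))]^k φ(x) dx.

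| Tests | ρ = 0 | ρ = 0.5 | ρ = 0.7 |
|---|---|---|---|
| 2 | 9.8% | 9.1% | 8.4% |
| 3 | 14.3% | 12.5% | 10.9% |
| 4 | 18.5% | 15.6% | 13.0% |

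At ρ = 0.9 the four-test figure is still 9.4%.

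**4. Errors favouring losartan only.** The claim at stake is benefit, so only the favourable tail counts, at 2.5% per test. Four independent tests give 1 − 0.975^4 = 9.6%. With correlation the figures are 7.8% (ρ = 0.5) and 6.5% (ρ = 0.7), against 2.5% for one test.

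**5. If all four tests had to be significant.** The two-sided error is 0.05^4, effectively zero, under independence, 0.15% at ρ = 0.5 and 0.58% at ρ = 0.7.

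**6. Cost of the alternatives.** Bonferroni over four tests (0.0125 each) holds the family-wise error at or below 4.9%. By the normal formula, collagen power falls to 0.38 / 0.55 / 0.71 / 0.84 for differences 0.5 / 0.6 / 0.7 / 0.8; by exact t, power for 0.7 falls from 0.85 to 0.68. A single named lead test, or a fixed sequence starting with it, holds 5% and leaves the lead test at full alpha.

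**The case against.** The strongest reply is that no success rule is written, so no error rate can be attributed to the plan. A reader might infer that the trial's false-positive rate is 13-19% rather than 5%. The documents do not support that as a fact: they do not state that four separate tests will be run or that any one suffices, and under an all-must-succeed rule the error is below 1%. That part of the reply stands, and the figures here are conditional. It does not remove the gap, because the range is wide precisely because the rule is missing.

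The four-test count is partly inferred. No passage says that FRCn integrity will be measured in gut; section 2.1 describes lymphoid tissue as covering lymph node and gut, while section 2.2 speaks of the lymph-node network. With three tests the range is 10.9-14.3%, and with the two named measures 8.4-9.8%.

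The two-sided figures also include significant results against losartan, which could not support a claim of benefit. This objection holds, and the directional figures answer it.

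A reader might count months 12 and 30 as separate tests and reach higher rates. Section 11.1 does not support this: it plans a longitudinal model comparing rates of change, not a test at each visit. Nor do the documents say that ileum and rectum will be tested separately.

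Finally, this is a small mechanistic trial, and leaving secondary biomarkers unadjusted is a defensible choice. The point is confined to the primary endpoint.

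**Conclusion.** The point holds as a gap in specification. Two unranked measures and two tissues serve the primary endpoint, and the plan has no lead test, success rule or multiplicity control.

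Its size depends on how the silence is filled. Where any one test suffices, the two-sided family-wise error is about 8-10% for two tests and 13-19% for four; in losartan's favour, the four-test figure is about 6.5-10% against a nominal 2.5%. These figures assume two-sided 0.05 (inferred from the power table), equal correlations of 0 to 0.7, and all nulls true. The gap should be closed before unblinding. It does not show that the trial will make a false claim at any particular rate.

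**What to change.** In section 11.5, before unblinding, name one primary test at two-sided 0.05: the measure, the tissue and the contrast from the section 11.1 mixed model. One suitable choice is the treatment effect on lymph-node collagen. Collagen is the only measure powered in section 11.2, but that section names no tissue or time point, so the choice should be justified on its own terms and not presented as already made there.

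Then list the remaining combinations (for example lymph-node FRCn, gut collagen and, if it is measured, gut FRCn) and test them in that fixed order at 0.05, stopping at the first non-significant result. State whether ileum and rectum are pooled.

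The change needs only analysis-plan wording: no extra subjects, biopsies or visits. The lead test keeps its full alpha, so the section 11.2 power is not reduced by the change, to the extent that the 0.81 SD applies to the chosen tissue and contrast. The downside is that later measures cannot be claimed as primary if an earlier step fails. Another lead measure or tissue would serve equally well, provided it is fixed in advance.

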12. QUALITY CONTROL AND QUALITY ASSURANCE

Please refer to detailed Site Quality Management Plan and Manual of Procedures in the grant application appendix, which is maintained in the study records, for quality control and assurance protocols.

13. ETHICS/PROTECTION OF HUMAN SUBJECTS

13.1 DAIDS Protocol Registration

Prior to implementation of this protocol, and any subsequent full version amendments, each site must have the protocol and the protocol informed consent form(s) approved, as appropriate, by their local institutional review board (IRB)/ethics committee (EC) and any other applicable regulatory entity (RE). Upon receiving final approval, sites will submit all required protocol registration documents to the DAIDS Protocol Registration Office (DAIDS PRO) at the Regulatory Support Center (RSC). The DAIDS PRO will review the submitted protocol registration packet to ensure that all of the required documents have been received.

Site-specific informed consent forms (ICFs) *WILL NOT* be reviewed or approved by the DAIDS PRO, and sites will receive an Initial Registration Notification when the DAIDS PRO receives a complete registration packet. Receipt of an Initial Registration Notification indicates successful completion of the protocol registration process. Sites will not receive any additional notifications from the DAIDS PRO for the initial protocol registration. A copy of the Initial Registration Notification should be retained in the site's regulatory files.

Upon receiving final IRB/EC and any other applicable RE approval(s) for an amendment, sites should implement the amendment immediately. Sites are required to submit an amendment registration packet to the DAIDS PRO at the RSC. The DAIDS PRO will review the submitted protocol registration packet to ensure that all the required documents have been received. Site-specific ICF(s) *WILL NOT* be reviewed and approved by the DAIDS PRO and sites will receive an Amendment Registration Notification when the DAIDS PRO receives a complete registration packet. A copy of the Amendment Registration Notification should be retained in the site's regulatory files.

For additional information on the protocol registration process and specific documents required for initial and amendment registrations, refer to the current version of the DAIDS Protocol Registration Manual.

13.2 Institutional Review Board

The investigator will ensure that this study is conducted in full conformity with the current revision of the Declaration of Helsinki, or with the International Conference for Harmonization Good Clinical Practice (ICH-GCP) regulations and guidelines, whichever affords the greater protection to the subject. This protocol and associated informed consent documents must be reviewed and approved by the University of Minnesota Institutional Review Board prior to protocol implementation.

13.3 Informed Consent Process

All participants participating in this study will be required to sign an IRB approved informed consent form. Participants who enroll in any of the sub-studies will also sign an additional consent form specific to each applicable sub-study. Prior to signing the consent form(s), the participants will meet with designated study staff who has been specially trained in obtaining informed consent. The participant will review the consent form in detail with the designated study staff and have the chance to ask questions. The study coordinator will then ask the participant questions to ensure that they understand the information presented in the consent form. The rights and welfare of the participants will be protected by emphasizing to them that the

quality of their medical care will not be adversely affected if they decline to participate in this study. Participants will be given time to consider the risks and benefits of participating. A copy of the informed consent document will be given to the participants for their records. The participants may withdraw consent at any time throughout the course of the trial. Consent forms for HIV infected and HIV uninfected (control) participants are included in this application.

13.4 Participant Confidentiality

A Certificate of Confidentiality will be obtained and all information that identifies study subjects will be handled in accordance with regulatory bodies including HIPAA regulations and the University of Minnesota's IRB. Information will be made available to the PI and designated study staff who directly participate in the research visits. In addition, information may be reviewed by the NIH, the Office For Human Research Protections and the IRB. Prior to screening, participants in this study will sign an authorization to use or disclose protected health information for research purposes. All staff will have been trained in the use of protected health information. Subjects will be assigned to a subject ID number and a link between identifiers will be maintained in a log. This log will be kept in a locked cabinet in a secure office. Only the PI and designated study staff will have access to this link.

13.5 Study Discontinuation

After study completion or in the event that the study is discontinued, subjects will stop taking study agents (for the HIV group: losartan or placebo; for controls: Stribild and Prezista).

14. DATA HANDLING AND RECORD KEEPING

14.1 Data Management Responsibilities

Data collection is the responsibility of the clinical research staff under the supervision of the PI, [name]. Study data will be recorded in study progress notes. Explanations will be mandated for any missing data. Study records will be retained according to federal regulations. For further detailed description of data management please refer to the Manual of Procedures and Data Management Plan maintained in the study files.

14.2 Source documents and Access to Source Data

In accordance with NIH policy we will make any source data accumulated as a result of this program available to others in a timely and reasonable fashion. We will make data available at the time it is accepted for publication. Written requests for access to data before publication can be made to the administrative core and, if reasonable, data will be forwarded to the individual(s) requesting access.

14.3 Quality Control and Quality Assurance

We have designed a multi-step process to ensure data quality and accuracy. Clinical data will be collected into a standardized CRF that includes collection of source documents from the clinical laboratory performing the assays. Designated study staff will enter this data in real-time into our database. Data generated from [name] laboratory, [name] laboratory, [name] laboratory, [name] laboratory, and [name] laboratory will be entered into the database by the research staff in the laboratory. In addition, a written report of the data with a full accounting of how the data was generated, how much sample was used, and any unusual circumstances surrounding the generation of data (need for repeated experiments, reason for rejecting data from a data set, specimen handling problems, etc.) will be sent on a monthly basis to designated study staff. They will place a copy of the written report into the study chart of each individual

participant with data in the report and will scan it into the database, which will contain links back to the subject and the laboratory. Designated study staff will conduct monthly audits of a randomly selected series of 10 subject study charts to compare source documentation with data entered locally and at remote laboratories. Discrepancies will be resolved immediately. If an error rate of data entry of more than 3% is discovered for an individual or a laboratory, we will conduct a full audit of data from that person or that site. We prefer to have data entered by the investigator performing the research (as opposed to a data entry person working off faxed records) because we have found that data is available for discussion more rapidly and this fosters better collaboration and a more interactive research environment.

15. PUBLICATION POLICY

Publication of the results of this trial will be governed by NIAID publication policies. Any presentation, abstract, or manuscript will be made available for review by the NIAID supporters prior to submission.

17. APPENDIX I

MRI Sub-study

The purpose of the study is to develop new ways to acquire and analyze MRI data to characterize the structural and functional changes of the body between the normal and disease state. This information would be valuable if and when the developed methods are incorporated into future clinical studies to help guide and monitor therapeutic interventions. The methods being developed will be experimental and will only be used for research purposes. We think it possible that this non-invasive procedure might someday be used as a biomarker in studies of anti-fibrotic therapy in HIV infection.

We will explore several standard and novel contrasts and their parametric maps to assess lymph flow and collagen amounts in LT. MRI studies will be performed on a 3 Tesla and/or 7T imaging systems (Siemens Medical Solutions, Erlangen, Germany). To acquire data, surface or surface array coils will be used for signal reception.

Protocol:

- 1) Scout imaging to localize target anatomy. (1 minute)
- 2) Maps of B1+ by the 3D AFI technique (4 minutes)
- 3) T2 weighted imaging (turbo spin echo, 0.5x0.5x3.0 mm³ resolution in the three planes) (10 minutes)
- 4) T2 mapping with the methods by Liney et al. (5 minutes)
- 5) T1 mapping with DESPOT (72) (5 minutes)
- 6) Diffusion weighted imaging (DWI), using a standard single shot approach in three orthogonal directions with multiple diffusion encoding b-values (e.g. 0, 50, 400 and 800 s/mm²) allowing the calculation of ADC— how long? (5 minutes)
- 7) Magnetization transfer (MT) using GRE readout, with T1sat mapping (10 minutes)
- 8) T1p mapping, using GRE readout (not clear, the application mention them, but then does not give details) (5 minutes)
- 9) T2p mapping, using GRE readout (not clear, the application mentions them, but then does not give details) (5 minutes)
- 10) RAFFn mapping using GRE readout (10 minutes)

Inclusion Criteria: (See Section 5.2)

Same as parent losartan study.

Exclusion Criteria:

Exclusion criteria will be assessed during a safety screening interview and during final consent. A questionnaire will be provided regarding general health and exclusion/inclusion criteria. The investigator doing the interview will determine if any of the exclusion criteria apply. Subjects will be asked:

- 1) To describe any previous surgeries to help subjects and study staff open a dialogue as to any possible contraindications listed in the yes/no section below.
- 2) If they are claustrophobic and to rate the severity.
- 3) If they wear hearing aids and if they can be removed for the scan.
- 4) If they have a transdermal delivery system, and if yes where is it located and if it can be removed for the study.
- 5) If they wear colored contact lenses and, if yes, can they be removed for the study.
- 6) To provide a list of medications, dosages and time of last dose for medicines taken regularly.

- 7) To identify if they have any pre-existing medical conditions including Hypertension, Hypotension, Diabetes, Cardiovascular Disease and Fever.
- 8) To identify if they ever had an operation.
- 9) To indicate if they have ever been injured by a metallic foreign body which was never removed.
- 10) If they wear braces and/or if they have removable bridgework, false teeth or a permanent retainer.
- 11) If they have any tattoos, non-removable body piercings or hair extensions.
- 12) If they are currently using/wearing an IUD or diaphragm.
- 13) If they have any reason to believe they are pregnant. (If the subjects are unsure about their pregnancy status, test kits will be available to subjects).

In addition, a set of yes/no questions will be asked in the screening form for the participant to confirm or deny the presence of items that may be hazardous to their safety and/or some interfere with the MRI examination, including:

- Yes No Cardiac pacemaker
- Yes No Implanted cardiac defibrillator
- Yes No Carotid artery vascular clamp
- Yes No Intravascular stents, filters, or coils
- Yes No Aortic clip
- Yes No Internal pacing wires
- Yes No Vascular access port and/or catheter
- Yes No Swan-Ganz catheter
- Yes No Shunt (spinal or intraventricular)
- Yes No Aneurysm clip(s)
- Yes No Neurostimulator
- Yes No Electrodes (on body, head, or brain)
- Yes No Heart valve prosthesis
- Yes No Any type of prosthesis (eye, penile, etc.)
- Yes No Artificial limb or joint replacement
- Yes No Bone growth/fusion stimulator
- Yes No Bone/joint pin, screw, nail, wire, plate
- Yes No Metal rods in bones
- Yes No Harrington rods (spine)
- Yes No Metal or wire mesh implants
- Yes No Wire sutures or surgical staples
- Yes No Insulin pump or infusion device
- Yes No Any metal fragments (i.e. metal shop)
- Yes No Any implant held in place by a magnet
- Yes No Cochlear, otologic, or ear implant

RISKS AND BENEFITS:

NOTE: Appendix F's for both 3T and 7T systems are on file at the IRB and will not need to be submitted with this addendum.

Other Potential Risks.

- 1) Magnetic Field in the MRI (subject environment)
- 2) Metallic objects carried into the MRI room
- 3) Other energies, such as radiofrequency pulses, or rapid changes in the field strength

- 4) Displacement of Implanted metallic devices
- 5) Acoustic noise

Any risks from high magnetic field strength that has been identified as a concern by the FDA's office of device evaluation, has been addressed by our researchers, who performed numerous animal experiments. The results indicate non-significant risks (either short term or long term) at these magnetic field strengths (3T/7T).

Data over the last 10+ years indicate that the 7 Tesla magnetic field does not pose a significant risk to human volunteers. Metallic objects that are entered into the magnetic field can accelerate into the magnet potentially causing damage to the magnet or persons in the magnet room.

In addition, implanted metallic objects can be displaced. The acoustic noise generated by the scanner without ear protection could possibly impose damage to a person's hearing.

Finally, radiofrequency pulses impart small amounts of energy into the subject, and needs to be monitored by both hardware and software monitor to prevent inadvertent application of significant energies which may result in heating.

Most people experience no ill effects from the strong magnetic field, but some people report dizziness, mild nausea, headache, a metallic taste in their mouth, or sensations of flashing lights. These symptoms, if present, subside shortly after leaving the magnet. No serious ill effects have been reported to date at any site operating at 7T. If any sensations experienced cause discomfort or pain, informing the researcher will terminate the ongoing study and the subject will be taken out of the magnetic field.

The risk of metallic objects being carried into the magnet room by subjects has been addressed by having volunteers remove all jewelry and valuables (keys, hair pins, coins, glasses, watches, etc.) for secure storage in a locker provided to them, prior to entering the magnet room.

All risk of other energies involved in MRI imaging are controlled such that they are not a significant risk and are substantially equivalent to clinical MRI systems, such as the Philips and Siemens devices currently in use at the University of Minnesota Medical Center, Fairview. These factors are in compliance with FDA guidelines.

In addition, there are safety monitors in the MRI instrument that will prevent the machine from running if these energies exceed the FDA levels. Risks posed to persons with implanted devices are avoided by exclusion of such persons from the study. Any unknown risks posed to fetuses are avoided by exclusion of pregnant women. Acoustic noise is reduced to FDA acceptable levels by having the subjects wear ear plugs, providing padding around the subject ears, and by additional noise reduction foam place inside the magnet itself. The acoustic noise has been carefully measured using a special probe inside the magnet.

MRI scans have become a routine diagnostic tool widely used in medicine. Based on more than two decades of experience with this technique, appropriate guidelines exist for its use to minimize the risks of the study. Although there is no direct benefit to the research subjects, the parameters and research data garnered from the studies will lead to being able to make much improved clinical and diagnostic decisions. With minimal risk to the subjects, this research and the MRI instruments will allow us to obtain improved anatomic and functional throughout the human body. Twenty years of research at 4 tesla and 15 years at 7 Tesla has established this type of research as extremely safe, as well as extremely beneficial to the scientific and clinical communities.

There are no direct benefits to the individuals participating in this study as subjects. However, the new methods under development may provide novel biomarkers for monitoring disease progression and treatment response, aid in the development and evaluation of novel interventions, and/or provide unique tools to aid in the diagnosis and prognosis of disease.

INFORMED CONSENT PROCESS:

Upon arrival at the CMRR, the subject will be greeted by research staff, provided the consent and MRI safety screening forms and given a brief description of the study that will be conducted that day. Specific details of the study which will be reviewed including:

- the field strength of the study (3T or 7T)
- the region of the body that will be studied
- the RF coils that will be used
- any additional hardware such as ECG leads or respiratory monitoring equipment that will be necessary
- any particular tasks that they may be asked to perform such as breath holding during the MRI procedure.

After this introduction the subject will then be given an opportunity to read the consent form and ask questions. The researcher will provide the participant ample time to decide whether or not to participate. The researcher will also assess whether the participant understands the study's procedures and will stress the voluntary nature of the experiment. In addition, the subject will be reminded that this is purely a research study and that the data acquired cannot be used in place of standard imaging obtained through their physician.

Volunteers will be given the study specific consent form upon arriving at the CMRR at which time the investigator will detail the specific goals for the study that day and provide any study specific instructions.

The investigator will give the participant ample time to review the informed consent document. This may entail waiting with the subject while they review the material or leaving the room if they need more time to consider the study. When the participant has finished reading the document and signs (or chooses not to sign) it, they will notify the researcher. Participant questions will be answered prior to their consenting.

One of the investigators listed on the protocol will obtain informed consent. Usually it will be the individual who will be performing the MRI scan.

[name] – Associate Professor – already trained and running similar studies

[name] – Associate Professor – already trained and running similar studies

[name] – Associate Professor – already trained and running similar studies

[name] – Research Nurse – already trained and consenting on similar protocols

The subject will always provide the informed consent or the study will not be performed.

As described above, the investigator(s) will give the participant ample time to review the informed consent document. This may entail leaving the room if they need more time to consider the study reducing any pressure to sign it. Subjects are also instructed that they may terminate participation at any time without prejudice.
